14.4 Electrocardiogram (ECG)

Electrocardiograms are performed at Baseline, Weeks 4, 12, 28 and 52/ET visits. All tracings will be evaluated by a central reading laboratory. ECG data summaries will be performed using the centrally evaluated data.

Observed values of ECG variables (heart rate, PR interval, RR interval, QRS interval, QT interval, and QTc intervals) and the changes from Baseline at each assessment timepoint will be summarized at Baseline and each scheduled post-Baseline visit.

QTc intervals include QTcB (Bazett’s formula) and QTcF (Fridericia’s formula). QTcF will also be categorized into the following categories (msec) and the number and percentage of subjects in each category will be summarized at each scheduled visit and overall post-Baseline maximum:

- Observed: ≤450, 451 to 480, 481 to 500, and >500
- Change from Baseline: ≤10, 11 to 30, 31 to 60, and >60

Electrocardiogram values will be considered PCI if they meet the criteria listed in [Table 8](#). The number and percentage of subjects with post-Baseline PCI values will be summarized at each scheduled post-Baseline visit and for overall post-Baseline. For the overall post-Baseline summaries, all post-Baseline values will be considered, including unscheduled and out of window values. Subjects with multiple PCI values for a given parameter will be counted only once for that parameter. For the by-visit summary, the numerator for the percentage is the number of subjects with a post-Baseline PCI ECG for the given parameter, visit and double-blind treatment group and the denominator is the number of subjects with non-missing values for the given parameter, visit and double-blind treatment group. For the

overall post-Baseline summary, the numerator for the percentage is the number of subjects with at least 1 post-Baseline PCI ECG for the given parameter and double-blind treatment group and the denominator is the number of subjects with at least 1 post-Baseline ECG value for the given parameter and double-blind treatment group. A listing of all PCI values in study ACP-103-033 will be provided. This listing will include all observations from study ACP-103-033 for those subjects and parameters for which at least 1 PCI value (including Baseline) was observed

Table 8 Criteria for Potentially Clinically Important ECG Values

ECG Parameter	Unit	High PCI Criteria
QRS Interval	msec	≥120
PR Interval	msec	≥220
QTcB or QTcF	msec	>500
QTcB or QTcF: change from Baseline	>60 msec	

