included dyspepsia, nausea, constipation, and vomiting; severe nausea and vomiting were dose limiting in a few cases. Reported psychiatric conditions included such events as agitation, insomnia, and confusional state. In controlled studies of pimavanserin in subjects with PDP, the most frequent TEAEs experienced by subjects in the pimavanserin 34 mg group compared with the placebo group were urinary tract infection (UTI) (7.4% pimavanserin 34 mg vs. 6.9% placebo), nausea (6.9% pimavanserin 34 mg vs. 4.3% placebo), peripheral edema (6.9% pimavanserin 34 mg, 2.2% placebo), fall (6.4% pimavanserin 34 mg vs. 9.1% placebo), and confusional state (5.9% pimavanserin 34 mg vs. 2.6% placebo). In the long-term open-label studies in subjects with PDP, the most frequent AEs include fall (29.3%), UTI (18.5%), hallucination (14.5%), decreased weight (12.4%), and confusional state (11.0%). It is difficult to interpret these incidence rates in the absence of a concurrent control group, but the overall incidence appears within what would be expected in subjects with the underlying neurodegenerative disease, psychosis, and advanced age.

Clinical and non-clinical safety pharmacology studies of pimavanserin suggest a potential risk for QT prolongation. The magnitude of effect in humans has been assessed in a thorough QT study with doses of pimavanserin ranging from 17 to 68 mg and in the Phase 3 PDP program with a clinical dose of 34 mg. There was observed an average prolongation of approximately 5-8 milliseconds (ms). No clinically significant patterns have been observed in serious adverse events (SAEs) and there has been no evidence of pimavanserin-related laboratory abnormalities. As of 30 October 2015, 67 subjects have died during study participation with the majority of deaths considered not related or unlikely related to study drug. Five of these deaths occurred in 6-week double-blind studies (1 subject received placebo, 1 subject received 8.5 mg pimavanserin, and 3 subjects received 34 mg pimavanserin), and 62 deaths occurred in the multi-year, long-term open-label extension studies where the majority of subjects had been treated with pimavanserin for greater than 2 years.

Additional information is provided in the Investigator's Brochure.

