4.1.1 Inclusion Criteria

1. Can understand the nature of the trial and protocol requirements and provide signed informed consent and can understand and sign other forms necessary for participation in the trial (e.g., the Health Insurance Portability and Accountability Act [HIPAA] authorization form in the United States). The following requirements for consent must be met:
 - from the subject, if the subject is deemed competent to provide informed consent
 - from an appropriate person according to national and local regulations (e.g., the subject's legally authorized representative [LAR] with the subject's assent), if the subject is deemed not competent to provide informed consent
2. Lives at home or in an assisted living or care facility (but has the capacity to visit the clinic as an outpatient).

3. Has a designated study partner/caregiver (e.g., relative, housemate, close personal friend, or professional caregiver) who is in contact with the subject at least 3 times a week on 3 separate days. The study partner/caregiver should:
 - be willing and able to accompany the subject to all clinic visits,
 - be capable of routinely monitoring and reporting study drug use,
 - be regarded by the Investigator as sufficiently informed to report accurately on the subject's behavioral and functional status.
4. The subject's study partner/caregiver provides written agreement that they understand the study, including the role of the study partner/caregiver and will participate in the study
5. Both subject and study partner/caregiver are fluent in and able to read the local language in which study assessments are administered at the clinical site
6. Both subject and study partner/caregiver are willing and able to participate in all scheduled evaluations and complete all required tests
7. Must complete the Week 12 visit in Study ACP-103-032 while continuing to take his/her assigned dose of blinded study drug
8. If female, must be of non-childbearing potential (defined as either surgically sterilized or at least 1 year postmenopausal) or must agree to use a clinically acceptable method of contraception (e.g., oral, intrauterine device [IUD; diaphragm], injectable, transdermal or implantable contraception) or abstinence during the study, and 1 month following completion of the study. Females of childbearing potential must have a negative urine human chorionic gonadotropin (hCG) pregnancy test at Baseline.

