9.7.4 Vital Signs and Body Weight

Descriptive statistics for vital signs and body weight, including changes from baseline, will be tabulated by treatment group and timepoint. The number and percentage of subjects with changes from baseline (increases and decreases separately) in body weight of 7% or more will also be provided.

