5.3 Analysis Visit Windows

In general, the open-label Baseline assessment will be defined as the last non-missing assessment, including those from repeated and unscheduled measurements, before or on the first open-label dose date. Exceptions to this definition will be handled on a case by case basis.

Efficacy and safety assessments will be summarized by analysis visit as presented in Table 4 below.

Table 4 Analysis Visit Windows

Open-label (OL) Analysis Visit Name	Target Study Day¹	Study Day Interval
OL Baseline	1	≤1(based on the first open-label dose date)
OL Week 2	15	2 to 21
OL Week 4	29	22 to 42
OL Week 8	57	43 to 70
OL Week 12	85	71 to 112

OL Week 20	141	113 to 168
OL Week 28	197	169 to 224
OL Week 36	253	225 to 280
OL Week 44	309	281 to 336
OL Week 52	365	337 to 379
OL Follow-up	395	380 – maximum

¹ If the assessment date \geq first open-label dose date, study day = assessment date – first open-label dose date + 1; otherwise study day = assessment date – first open-label dose date. Study day 1 is the first open-label dose date.

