14 SAFETY ANALYSES

The safety summaries will be presented based on the Safety Analysis Set. Safety variables include AEs, clinical laboratory variables, vital signs, physical examinations, ECG and GCAS variables. Safety variables will be summarized by double-blind treatment group and overall using descriptive statistics. For each continuous measure in clinical laboratory variables, vital signs, and electrocardiogram, change from Baseline results will be presented in two ways as specified in [Section 5.1](#).

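### The SAP does not name the Baseline for its QTcF-change and 7% weight counts, and the default is an on-drug value for subjects from the parent study's pimavanserin arms

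*SAP*

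**What the plan says.** SAP 14.4 sorts QTcF at each scheduled visit, and at the overall post-Baseline maximum, in two ways. One uses the value itself ("Observed: ≤450, 451 to 480, 481 to 500, and >500"), the other its change ("Change from Baseline: ≤10, 11 to 30, 31 to 60, and >60"). Table 8 adds a potentially clinically important (PCI) criterion of more than 60 msec for "QTcB or QTcF: change from Baseline". Table 7 in SAP 14.3 flags weight change of 7% or more in either direction. This follows protocol 9.7.4, which asks for "changes from baseline (increases and decreases separately) in body weight of 7% or more". None of these places says which Baseline is meant.

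SAP 5.2 takes Baseline assessments from the parent study's Week 12 visit, and protocol 6.2 says the same for safety assessments. SAP 5.3 gives the only operational definition, with the day of first dosing in the extension as its cut-off: "the open-label Baseline assessment will be defined as the last non-missing assessment, including those from repeated and unscheduled measurements, before or on the first open-label" (quotation cut short here).

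The SAP does use a second reference elsewhere. SAP 14 states: "For each continuous measure in clinical laboratory variables, vital signs, and electrocardiogram, change from Baseline results will be presented in two ways". SAP 5.1 sets out the two ways: from the ACP-103-033 Baseline and from the ACP-103-032 Baseline. Protocol 9.1 has a third, from the Baseline preceding the first pimavanserin dose in whichever study that occurred. The SAP leaves it out, and section 19 reports no changes from the protocol.

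**The concern.** Inclusion criterion 7 reads: "Must complete the Week 12 visit in Study ACP-103-032 while continuing to take his/her assigned dose of blinded study drug". That visit is the extension's Baseline visit, and no washout is described. Subjects from the parent 20 mg and 34 mg arms therefore enter with an ECG and weight taken after about 12 weeks on pimavanserin. Subjects from the placebo arm enter with drug-free values.

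If the change counts use the open-label Baseline, they compare on-drug with on-drug in the first group and on-drug with drug-free in the second. The overall column required by SAP 14 mixes the two. Clinically important changes in ECG and weight are a named safety endpoint (SAP 2.1.2), and QT prolongation is a potential risk that protocol 1.2 itself raises. A count of large QTcF changes that has already absorbed the drug's average effect is less sensitive to that risk.

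A hypothetical subject shows the mechanism. Suppose QTcF is 390 ms before any drug, 430 ms at open-label Baseline and 452 ms later. The change is 452 − 390 = 62 ms from the pre-drug value, which meets Table 8. From the open-label Baseline it is 452 − 430 = 22 ms, which does not. The value is also well below 500 ms.

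**Working it through.** The documents give no outlier rate and no SD for QTcF change, so there is no figure to reproduce. The calculation is an illustration.

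**Inputs**
- Mean drug effect on QT: about 5 to 8 ms (protocol 1.2).
- Cut-offs: above 30 ms (the top two change categories) and above 60 ms (SAP 14.4, Table 8).
- Post-Baseline ECGs: four, at Weeks 4, 12, 28 and 52 (SAP 14.4).
- SD of single-ECG QTcF change: **assumed** 15 to 20 ms, with 25 ms as a wider check.
- Former pimavanserin subjects: **assumed** 74 = 2/3 × 111. The 111 is the planned maximum. The split by parent arm is not given.

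**Single visit.** P(change > c) = 1 − Φ((c − m)/SD). Take m = 0 for an on-drug Baseline (same exposure at both times) and m = 5 or 8 for a pre-drug Baseline.

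For c = 30:
- SD 15: 1 − Φ(30/15) = 2.3%. Pre-drug: 1 − Φ(25/15) = 4.8% to 1 − Φ(22/15) = 7.1%.
- SD 20: 1 − Φ(30/20) = 6.7%. Pre-drug: 1 − Φ(25/20) = 10.6% to 1 − Φ(22/20) = 13.6%.

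For c = 60:
- SD 15: 1 − Φ(60/15) = 0.003%. Pre-drug: 0.012% to 0.026%.
- SD 20: 1 − Φ(60/20) = 0.135%. Pre-drug: 0.298% to 0.466%.

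**Maximum of four ECGs.** Each change is e_t − e_0 + m. Every e has SD equal to the change SD divided by √2, and e_0 is shared by the four visits (1,000,000 simulated subjects). Expected subjects among 74:

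| SD (ms) | >30 ms, on-drug | >30 ms, pre-drug | >60 ms, on-drug | >60 ms, pre-drug |
|---|---|---|---|---|
| 15 | 5.3 | 10.2-14.5 | 0.01 | 0.04-0.08 |
| 20 | 13.7 | 20.1-24.5 | 0.36 | 0.78-1.20 |
| 25 | 21.4 | 27.6-31.6 | 2.07 | 3.39-4.44 |

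At SD 15 to 20 the largest shortfall above 60 ms is 1.20 − 0.36 = 0.84 subjects. At SD 25 it is 3.39 − 2.07 = 1.3 to 4.44 − 2.07 = 2.4.

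**Weight.** The documents give no weight change during the parent study. Assume a change SD of 5% and no mean change during the extension. The chance of a loss of 7% or more from the open-label Baseline is Φ(−7/5) = 8.1%. From the parent Baseline it is Φ(−5/5) = 15.9% if 2% was lost on average during the parent study, and Φ(−9/5) = 3.6% if 2% was gained. The direction depends on a quantity the documents do not supply.

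**The case against.** The strongest reply is that the SAP never restricts these criteria to the open-label Baseline. QTcF and weight are continuous measures, and a categorised change is arguably a change-from-Baseline result, so the two-way rule could be read to cover it. A reader might infer that the SAP prescribes an open-label-only rule, and the documents do not support that. What they show is an unspecified Baseline with a default. The default still matters: the categories and PCI counts are specified separately from the continuous summaries, and the PCI listings hold only ACP-103-033 observations.

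Other safeguards are real. The observed-value QTcF categories and the 500 msec criterion need no Baseline. Mean QTcF and weight changes will be shown from the parent Baseline. Results are given by parent treatment group, so the former placebo group, whose open-label Baseline is already pre-drug, can be read separately. Change since entering the extension is also a legitimate question. None of this shows which individuals in the former pimavanserin groups changed greatly from their pre-drug value.

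The size is also open to challenge. Every SD is assumed. The 5-8 ms comes from a thorough QT study at 17 to 68 mg and a 34 mg programme, so applying it to the 20 mg arm is a further assumption. Nor is the shift removed exactly: everyone restarts at 20 mg and may change dose, so exposure at a later ECG can differ from that at Baseline.

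**Conclusion.** The point holds for QTcF as a gap in specification whose default reading is the less sensitive one. In the former pimavanserin arms, counts of QTcF change above 30 ms would tend to be too low relative to a pre-drug reference, by a factor of about 1.6 to 3.1 per visit (13.6/6.7 = 2.0 and 10.6/6.7 = 1.6 at SD 20; 7.1/2.3 = 3.1 at SD 15). For the 60 msec criterion the relative effect is larger but rests on very small rates. The expected loss is under about one subject among an assumed 74, and exceeds that only at the wider SD of 25 ms. These figures depend on the assumed SD, normality, the 5-8 ms effect and similar exposure at Baseline and later ECGs.

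A reader might infer that weight outliers are under-counted too. The documents do not show this: the count could be too low or too high, and the point for weight is only which reference value is used. Nor do the former placebo subjects' counts suffer, since their open-label Baseline precedes any pimavanserin. The study is descriptive and tests no hypothesis, so this is a cheap improvement.

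**What to change.** In SAP 14.3 and 14.4, name the Baseline for each change-based category and each PCI criterion that contains a change. Tabulate each in two versions side by side:

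- against the last value before the first pimavanserin dose in either study, as in the third presentation of protocol 9.1 (parent Baseline for former pimavanserin subjects, extension Baseline for former placebo subjects);
- against the open-label Baseline.

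Using the parent Baseline for everyone would be a poorer choice, because it adds the 12-week placebo period to the former placebo subjects' changes. Protocol 9.1 words its third presentation for continuous measures, so its extension to the counts has to be written out.

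Add the pre-drug value to the PCI listings. Either restore the third presentation in SAP 5.1 or record its removal in section 19.

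The cost is SAP wording and an extra version of a few tables. The parent-study Baselines are already needed for the second presentation in SAP 5.1. The reported QTcF outlier rates may look slightly less favourable.

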	
status.
 
4. The subject's study partner/caregiver provides written agreement that they understand the study, including the role of the study partner/caregiver and will participate in the study5. Both subject and study partner/caregiver are fluent in and able to read the local language in which study assessments are administered at the clinical site6. Both subject and study partner/caregiver are willing and able to participate in all scheduled evaluations and complete all required tests7. Must complete the Week 12 visit in Study ACP-103-032 while continuing to take his/her assigned dose of blinded study drug8. If female, must be of non-childbearing potential (defined as either surgically sterilized or at least 1 year postmenopausal) or must agree to use a clinically acceptable method of contraception (e.g., oral, intrauterine device [IUD; diaphragm], injectable, transdermal or implantable contraception) or abstinence during the study, and 1 month following completion of the study. Females of childbearing potential must have a negative urine human chorionic gonadotropin (hCG) pregnancy test at Baseline 
Exclusion Criteria:
 
1. Is participating in another clinical trial (other than Study ACP-103-032) of any investigational drug, device, or intervention2. The Investigator determines that enrollment in the study would be detrimental to a subject's well-being3. The Investigator becomes aware of an impending and unexpected change in the subject's living situation (e.g., change in caregiver, change in facility, moving from home to facility, moving from one family member or caregiver's home to another) that s/he judges may cause a major disruption in the subject's behavior4. Subject or study partner/caregiver has an uncorrected medical condition (e.g., hearing, vision impairments) that would impair the ability to perform the study assessments.5. Subject is judged by the Investigator or the Medical Monitor to be inappropriate for the study6. Subject was significantly non-compliant in Study ACP-103-0327. Subject has had a QRS interval <120 ms and whose Fridericia's corrected QT interval (QTcF) is >460 ms at baseline OR subject has had a QRS interval ≥120 ms and QTcF is >480 ms at Baseline8. Has clinically significant laboratory abnormalities that in the judgment of the Investigator would jeopardize the safe participation of the subject in the study9. Subject has become bedridden or has any significant medical

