Number and percentage of subjects with potentially clinically important (PCI) laboratory values at each scheduled post-Baseline visits and overall post-Baseline will be summarized by Baseline status (all and within normal range) for selected parameters. PCI criteria are listed in [Table 5](#) and [Table 6](#). For the overall post-Baseline summaries, all post-Baseline values will be considered, including unscheduled and out of window values. Subjects with multiple PCI values for a given parameter will be counted only once for that parameter. For the by-visit summary, the numerator for the percentage is the number of subjects with a post-Baseline PCI laboratory value for the given parameter, visit and double-blind treatment group, and the denominator is the number of subjects with non-missing values for the given parameter, visit and double-blind treatment group. For the overall post-Baseline summary, the numerator for the percentage is the number of subjects with at least 1 post-Baseline PCI laboratory value for the given parameter and double-blind treatment group and the denominator is the number of subjects with at least 1 post-Baseline laboratory value for the given parameter and double-blind treatment group. For hemoglobin, hematocrit and uric acid, the count and percentage of subjects with PCI values will be presented for each gender as well as for both genders combined. A listing of all PCI values in study ACP-103-033 will be provided. This listing will include all observations from study ACP-103-033 for those subjects and parameters for which at least 1 PCI value (including Baseline) was observed.

Table 5 Criteria for Potentially Clinically Important Laboratory Values – Hematology and Chemistry

Analyte	Conventional Unit	Low PCI Criteria	High PCI Criteria	SI Unit	Low PCI Criteria	High PCI Criteria
Hematology (whole blood)						
Hemoglobin (male)	g/dL	<11	>18	g/L	<110	>180
Hemoglobin (female)	g/dL	<10	>17	g/L	<100	>170
Hematocrit (male)	%	<30	>55	L/L	<0.3	>0.55
Hematocrit (female)	%	<30	>50	L/L	<0.3	>0.5
Leukocyte (White Blood Cell Count)	x 10 ³ /uL	≤2.8	≥15	x 10 ⁹ /L	≤2.8	≥15
Neutrophils	x 10 ³ /uL	≤1.5	No upper limit	x 10 ⁹ /L	≤1.5	No upper limit
Platelet Count	x 10 ³ /uL	≤75	≥700	10 ⁹ /L	≤75	≥700
Chemistry (serum or plasma)						
ALT (SGPT)	U/L	No lower limit	≥3 X ULN	U/L	No lower limit	≥3 X ULN
AST (SGOT)	U/L	No lower limit	≥3 X ULN	U/L	No lower limit	≥3 X ULN
Total Bilirubin	mg/dL	No lower limit	≥1.5 ULN	umol/L	No lower limit	≥1.5 ULN

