14.3 Vital Signs

Vital signs are assessed at Baseline, Weeks 2, 4, 8, 12, 20, 28, 36, 44, and 52/ET visits.

Vital signs including weight, height (measured at ACP-103-032 Screening visit), and the derived BMI will be summarized using descriptive statistics at Baseline and all scheduled post-Baseline visits. The change from Baseline values will also be summarized at the scheduled post-Baseline visits.

Vital sign values will be considered PCI if they meet both the observed value criteria and the change from Baseline criteria listed in [Table 7](#). The number and percentage of subjects with post-Baseline values that are PCI will be summarized at each scheduled post-Baseline visit and for overall post-Baseline. For the overall post-Baseline summaries, all post-Baseline values will be considered, including unscheduled and out of window values. Subjects with multiple PCI values for a given parameter will be counted only once for that parameter. For the by-visit summary, the numerator for the percentage is the number of subjects with a post-Baseline PCI vital sign for the given parameter, visit and double-blind treatment group and the denominator is the number of subjects with non-missing values for the given parameter, visit and double-blind treatment group. For the overall post-Baseline summary, the numerator for the percentage is the number of subjects with at least 1 post-Baseline PCI vital sign for a given parameter and double-blind treatment group and the denominator is the number of subjects at least 1 post-Baseline vital sign for the given parameter and double-blind treatment group. A listing of all PCI values in study ACP-103-033 will be provided. This listing will include all observations from study ACP-103-033 for those subjects and parameters for which at least 1 PCI value (including Baseline) was observed.

Table 7 Criteria for Potentially Clinically Important Vital Signs

Vital Sign Parameter	Unit	Criteria ^a		
		Observed Value	And/Or	Change Relative to Baseline
Systolic blood pressure	mmHg	≥180	And	Increase of ≥20
		≤90	And	Decrease of ≥20
Diastolic blood pressure	mmHg	≥105	And	Increase of ≥15
		≤50	And	Decrease of ≥15
Pulse	bpm	≥120	And	Increase of ≥15
		≤50	And	Decrease of ≥15
Weight	kg	Not Applicable		Increase of ≥7%
				Decrease of ≥7%

^a A post-Baseline value is considered as a PCI value if it meets both criteria for observed value and change from Baseline.

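### SAP 14.4 counts QRS ≥120 ms and PR ≥220 ms after Baseline without regard to Baseline status, so these percentages mix pre-existing with new abnormalities

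*SAP*

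**What the plan says.** SAP 14.4 has one rule for potentially clinically important (PCI) ECG values: "Electrocardiogram values will be considered PCI if they meet the criteria listed in" Table 8. The QRS row reads "QRS Interval msec ≥120" and the PR row "PR Interval msec ≥220". Only the row labelled "QTcB or QTcF: change from Baseline" refers to Baseline, and it covers QTc alone. The output is then a count: "The number and percentage of subjects with post-Baseline PCI values will be summarized", by visit and overall. The overall numerator is every subject with a PCI value after Baseline. The denominator is every subject with any value after Baseline for that parameter.

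The SAP treats other safety data differently:

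- Laboratory PCI counts (SAP 14.2) are given "by Baseline status (all and within normal range) for selected parameters", and laboratory values also have shift tables.
- For vital signs (SAP 14.3), "Vital sign values will be considered PCI if they meet both the observed value criteria and the change from Baseline criteria".

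Exclusion criterion 7 (Protocol synopsis and 4.1.2) removes a subject with a wide QRS only in combination with a long QTcF: "OR subject has had a QRS interval ≥120 ms and QTcF is >480 ms". No criterion mentions PR. The safety endpoint in Protocol 2.1.3 and SAP 2.1.2 is clinically important change from Baseline, ECGs included.

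**The concern.** The QRS value that eligibility allows is the value that Table 8 flags. Protocol Appendix B also provides for subjects with bundle branch block or ventricular pacing, so the protocol itself anticipates such participants. Someone with a stable wide QRS or long PR meets the PCI rule before the first open-label dose and will usually meet it again afterwards.

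The study is uncontrolled and its purpose is safety, so these percentages are themselves a result. For QRS and PR the PCI table is the only categorical output. If it cannot distinguish subjects who crossed a threshold from subjects who arrived above it, it does not answer the question set by the endpoint.

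**Working it through.** The documents state no derived figure on this point, so there is nothing to reproduce. The check compares the rules and then illustrates their effect.

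**1. The rules side by side**

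| Data | Observed-value cut | Change from Baseline used | Split by Baseline status | Shift table |
|---|---|---|---|---|
| Laboratory (14.2) | yes | no | yes: all, and normal at Baseline | yes |
| Vital signs (14.3) | yes, except weight | yes | no | no |
| QTc (14.4) | >500 msec | separate row, >60 msec; QTcF change categories | no | no |
| QRS, PR (14.4) | ≥120; ≥220 msec | no | no | no |

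QRS and PR are the only parameters for which the count takes no account of Baseline. The >500 msec row is less exposed: exclusion criterion 7 keeps Baseline QTcF at or below 460 ms (narrow QRS) or 480 ms (wide QRS), so no eligible subject meets it at entry on QTcF.

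**2. One subject through the rule**

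Take QRS 130 ms at Baseline, QTcF within the limit, and QRS 130 ms at Week 4. The subject is eligible. The change is 130 − 130 = 0. The Week 4 value is ≥120, so the subject counts as post-Baseline PCI at Week 4 and overall.

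**3. Illustration of size, for one parameter at a time**

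Inputs:

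- N = 111, the planned maximum (Protocol 3.3, SAP 3.5).
- p, the proportion at or above the cut at Baseline: assumed 5-15%.
- r, the proportion of the remainder who newly cross it: assumed 0 or 2%.
- Pre-existing abnormality is assumed to persist, and every subject is assumed to have a post-Baseline ECG.

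Formulas:

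- count under the SAP = N·p + N·(1 − p)·r
- new cases = N·(1 − p)·r, out of N·(1 − p)

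With r = 0, the count is 111 × 0.05 = 5.55 to 111 × 0.15 = 16.65, about 6 to 17 subjects, none of them changed.

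With r = 2%:

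| p | Pre-existing | New | SAP count | SAP % | Pre-existing share |
|---|---|---|---|---|---|
| 5% | 5.55 | 105.45 × 0.02 = 2.1 | 7.7 | 6.9 | 72.5% |
| 10% | 11.1 | 99.9 × 0.02 = 2.0 | 13.1 | 11.8 | 84.7% |
| 15% | 16.65 | 94.35 × 0.02 = 1.9 | 18.5 | 16.7 | 89.8% |

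The proportion among subjects at risk is 2.0% in every row. At p = 5% the chance that at least one of 111 subjects enters above the cut is 1 − 0.95^111 = 99.7%.

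**4. Which Baseline**

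The open-label Baseline is carried over from Week 12 of ACP-103-032 (SAP 5.2), or is the last value on or before the first open-label dose (SAP 5.3). For the two former pimavanserin groups it is an on-drug value. Suppose such a subject was below the cut at the ACP-103-032 Baseline and above it from that study's Week 12 onward. A split on the open-label Baseline would treat the subject as pre-existing, although the abnormality appeared on drug. A split on that Baseline alone would therefore introduce an error of its own.

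**The case against.** The strongest reply is that the plan does not leave the reader without help. SAP 14.4 also summarizes changes from Baseline in PR and QRS by visit. It lists every ACP-103-033 observation, Baseline included, for each subject and parameter with a flagged value. With about 111 subjects that listing can be read by hand. The counts are openly defined and are not called new or treatment-emergent. No hypothesis is tested. The ECG risk that Protocol 1.2 describes is QT prolongation, which has change-based criteria, and Protocol 9.7.5 asks for categorical analysis of QTc only.

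Much of this stands and limits the point. A reader might infer that nothing separates prevalent from new abnormality, or that a real signal is hidden or a false one created. The documents do not support that, because the listing and the mean changes are there. A reader might also take the QRS and PR counts simply as prevalent conduction disease. For the former pimavanserin groups this is unsafe, because their open-label Baseline is already on drug. Nor may QRS and PR be pooled into one inflated count: the table reports each parameter separately.

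The reply does not remove the point. A mean change does not count subjects who cross a threshold. A listing gives no numerator or denominator, and this one omits the pre-drug ECG of subjects treated in ACP-103-032. The absence of a test is no answer where the descriptive percentages are the result. The laboratory precedent is similar but not identical: it restricts to values within the normal range at Baseline, not to values below the PCI cut.

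**Conclusion.** The point holds as a defect in the reporting of two parameters. As written, the QRS and PR PCI percentages combine pre-existing and new abnormalities and do not measure change from Baseline, which is the stated endpoint. This follows from the text and needs no assumption beyond the presence of at least one subject who enters above a cut and has a later ECG that is still above it.

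The size cannot be fixed from the documents. The 6-17 added subjects per parameter rest on an assumed prevalence of 5-15%, full enrolment of 111 and persistence of the abnormality. Eligibility shows that such subjects may enrol, not how many will, and values near a cut can fall either side of it. QTc is not affected in the same way, and no test or error rate is involved.

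**What to change.** In SAP 14.4, keep the all-subjects row and add, for QRS and PR separately, a row limited to subjects below that cut at Baseline, with those subjects as the denominator. A Baseline-by-worst-post-Baseline shift table would serve equally well.

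Name the Baseline and show the added row both ways:

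- against the ACP-103-033 Baseline;
- against the last value before the first pimavanserin dose, which is the ACP-103-032 Baseline for subjects given pimavanserin there and the ACP-103-033 Baseline for former placebo subjects.

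The second definition matches the third Baseline approach that Protocol 9.1 sets out for continuous measures. It keeps abnormalities that emerged during the parent study from being dropped. The text should also state whether ECGs from ACP-103-032 after that Baseline count towards the numerator.

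The cost is a few sentences and a few table rows, with no new data or visits. The downside is small denominators within groups. If 111 subjects divided evenly into three groups of 37 (an assumption), the same 5-15% prevalence would leave about 31-35 per group (37 × 0.85 = 31.5; 37 × 0.95 = 35.2).
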